Appendix 4: Rectal Function Assessment Score (R-FAS)

1.	Frequency of stools per day: □ 0-1 stool per day □ 2 stools per day □ 3 stools per day □ 4 or more stools per day
2.	Consistency of stools: ☐ All stools formed ☐ Stools Formed and loose ☐ Stools loose ☐ Watery stools
3.	Urgency of stools: ☐ No urgency ☐ Somewhat urgent ☐ Urgent ☐ Very urgent
4.	Abdominal discomfort: ☐ No discomfort ☐ Mild to moderate discomfort ☐ Somewhat severe discomfort ☐ Very severe discomfort
5.	Hemorrhoid discomfort: ☐ No discomfort ☐ Required mild treatments (i.e. tucks, sitz baths) ☐ Requires topical medication (i.e.Prep H, etc.) ☐ Requires oral analgesics or narcotics for relief
6.	Rectal bleeding ☐ No rectal bleeding ☐ Blood on toilet paper: 1 time per week ☐ 2-3 times per week ☐ ≥ 4 times per week
7.	Continence: ☐ Normal continence; able to control stool movement at all times ☐ Gas incontinence only; able to control stool movements but not gas ☐ Minor spotting or leakage of stool (up to coin size) about once per week ☐ Minor spotting or leakage of stool (up to coin sixe) more than once per week

Short Title: Q-Urol	Subject ID:	Subject Initials:
Version Date: 11APR2023		Date:
	` •	n coin size about once per week) n coin size more than once per week
8. Nighttime bowel mover from bed to have a bow □ 0 □ 1 □ 2 □ 3 □ 4 □ More than	`	er of nights in last week that you had to get up
"all done") ☐ Occasional multiple takes more than one	evacuations (about movement to finite vacuations (more to the movement to finite	han once a week feel like you're not "all done" or nish)
10. My Bowel Movements ☐ Better ☐ Worse ☐ Same ☐ Not Applicable	after radiation or	implant are:
 Patient Signature		

Short Title: Q-Urol	Subject ID:	Subject Initials:
Version Date: 11APR2023		Date:

Appendix 5: The Sexual Health Inventory for Men (SHIM) Questionnaire

- 1. How do you rate your confidence that you could get and keep an erection?
 - 1. Very low
 - 2. Low
 - 3. Moderate
 - 4. High
 - 5. Very high
- 2. When you had erections with sexual stimulation, how often were your erections hard enough for penetration (entering your partner)?
 - 0. No sexual activity
 - 1. Almost never or never
 - 2. A few times (much less than half the time)
 - 3. Sometimes (about half the time)
 - 4. Most times (much more than half the time)
 - 5. Almost always or always
- 3. During sexual intercourse, how often were you able to maintain your erection after you had penetrated (entered) your partner?
 - 0. Did not attempt intercourse
 - 1. Almost never or never
 - 2. A few times (much less than half the time)
 - 3. Sometimes (about half the time)
 - 4. Most times (much more than half the time)
 - 5. Almost always or always
- 4. During sexual intercourse, how difficult was it to maintain your erection to completion of intercourse?
 - 0. Did not attempt intercourse
 - 1. Extremely difficult
 - 2. Very difficult
 - 3. Difficult
 - 4. Slightly difficult
 - 5. Not difficult
- 5. When you attempted sexual intercourse, how often was it satisfactory for you?
 - 0. Did not attempt intercourse
 - 1. Almost never or never
 - 2. A few times (much less than half the time)
 - 3. Sometimes (about half the time)
 - 4. Most times (much more than half the time)
 - 5. Almost always or always

Short Title: Q-Urol	Subject ID:	Subject Initials:	
Version Date: 11APR2	2023	Date:	
	-		
Patient Signature		Date	
Total:			
SHIM Scores	You may have		
1-7	Severe ED		
8-11	Moderate ED		
12-16	Mild to Moderate ED		
17-21	Mild ED		
22-25	No signs of ED		
Research Team Mo	ember Signature	Date	

Version Date: 11APR2023

Appendix 6: Patient Dosing Diary

Subject ID:		Subject Initials:		
Week #:				
	otten outside of the 4	l-hour window, it should r	e every day (\pm 4 hours). If not be made up but rather,	
Date	Time	Number of capsules taken	Comments	
	:			
	:			
	:			
	:			
	:			
	:			
	:			
	:			
	:			
	:			
	:			
	:			
	:			
	:			
	:			
	:			
	:			
	:			
	:			
	:			
	:			
Patient Signature			Date	

Version Date: 11APR2023

Appendix 7: Pain Management Diary

Subject ID:	Subject Initials:		
Week #:			
Please record any use of me	dications intended for the managemen	t of prostate pain.	
Date	Medicatio	on Taken	
	Have you taken any medicat	ion today for prostate pain?	
	☐ Yes	□ No	
	Have you taken any medicat	ion today for prostate pain?	
	☐ Yes	□ No	
	Have you taken any medicat	ion today for prostate pain?	
	☐ Yes	□ No	
	Have you taken any medicat	ion today for prostate pain?	
	☐ Yes	□ No	
	Have you taken any medicat:	ion today for prostate pain?	
	☐ Yes	□ No	
	Have you taken any medicat:	ion today for prostate pain?	
	☐ Yes	□ No	
	Have you taken any medicat:	ion today for prostate pain?	
	☐ Yes	□ No	
	Have you taken any medicat:	ion today for prostate pain?	
	☐ Yes	□ No	
	Have you taken any medicat:	ion today for prostate pain?	
	☐ Yes	□ No	
	Have you taken any medicat:	ion today for prostate pain?	
	☐ Yes	□ No	
D. (*			
Patient Signature		Date	

Short Title: Q-Urol Version Date: 11APR2023

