1.2 Secondary Objective(s)

1.2.1 To assess Health-Related Quality of Life (HRQOL) in the urologic, rectal, sexual, hormonal, mental and overall physical domains of men receiving either placebo or supplement after definitive brachytherapy.

Secondary Endpoint: Patient questionnaires administered pre- and post-study therapy: The Expanded Prostate Cancer Index Composite (EPIC), The International Prostate Symptom Score (I-PSS), The Rectal Function Assessment Score (R-FAS), and the Sexual Health Inventory for Men (SHIM).

1.2.2 To assess if the Q-Urol has any significant impact on serum biomarkers of inflammation relative to placebo.

Secondary Endpoint: Inflammation markers pre and post brachytherapy: erythrocyte sedimentation rate, C-reactive protein, and prostate-specific antigen (PSA)

1.2.3 To access if the addition of Q-Urol introduces any additional toxicity relative to placebo.

Secondary Endpoint: Frequency of adverse events (AEs) will be collected and characterized by type, severity (as defined by CTCAE, version 5.0), seriousness, duration, and relationship to study treatment.

1.2.4 To assess the effect on prostatitis-related pain in men with localized prostate cancer following brachytherapy taking Q-Urol relative to placebo.

Secondary Endpoint: The number of days during the 28 days post-brachytherapy that any medication is taken for the treatment of prostate-related pain.

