7 TREATMENT PLAN

7.1 Administration Schedule

Patients will undergo Low Dose Radiation (LDR) brachytherapy with or without External Beam Radiation Therapy (EBRT) or High Dose Radiation (HDR) brachytherapy with EBRT. When LDR is used as monotherapy the isotope will be PD-103 prescribed at 125 Gy, when used as a combined modality with EBRT, the LDR brachytherapy will precede the EBRT, the isotope used will be PD 103 prescribed at 100Gy. HDR monotherapy will not be performed. The HDR + EBRT regimen will be a single fraction of Iridium-192 prescribed at 15Gy and will precede the EBRT. When EBRT is combined with LDR or HDR, the EBRT will only occur after the completion of the study drug regimen and toxicity evaluations for the primary endpoints.

On the day of but after brachytherapy, patients will self-administer two Q-Urol or placebo capsules by mouth with food twice daily. Doses should be taken at about the same time every day (\pm 4 hours) and recorded on the patient's dosing diary. Doses missed outside of the dosing window should not be made up but rather patients should be instructed to take their next dose at their regularly scheduled time.

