7.2.2 Preparation and Administration

Subjects will be provided enough Q-Urol/placebo for a full six weeks of treatment at the time of brachytherapy. Subjects will be instructed to self-administer the medication at home orally twice daily (every 12 hours \pm 4 hours) with food. Subjects should begin dosing the evening after brachytherapy placement. Subjects should not take extra medication for any reason nor should they re-administer in the case of vomiting after administration. If a dose is missed outside of the dosing window, the dose should not be made up.

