7.3.2 Prohibited Therapy

Medications or vaccinations specifically prohibited in the exclusion criteria are not allowed during the active treatment period. Patients are prohibited from receiving the following therapies during the treatment phase of this trial:

- Investigational agents, other than those utilized during study therapy.
- Radiation therapy other than the brachytherapy conducted in conjunction with this study.
- Herbal remedies, other than Q-Urol, defined as any substance derived from a botanical source, not prescribed by the physician that a patient is using without professional medical guidance with the intent of treating prostate specific conditions.
- Cyclosporine
- Digoxin
- Warfarin
- CYP2C8 substrates (e.g., repaglinide, paclitaxel, omeprazole, cisapride)

7.3.3 Allowed therapies to be used with caution and the discretion of the treating physician

- While on study therapy, the use of anticoagulants should be used with caution.
- Quercetin may have additive hypoglycemic effects when used with antidiabetic medications; use the combination with caution.
- Quercetin may have varying effects on CYP3A4; substrates of CYP3A4 with a narrow therapeutic index should be used with caution (Appendix 12)
- Quercetin may have additional blood pressure lowering effects when used with anti-hypertensive medications; use the combination with caution
- Quercetin may have inhibitory effects on CYP2C9, CYP2D6, OATP1B1, and P-gp; substrates of these with narrow therapeutic indexes should be used with caution (Appendix 12).

7.4 **Duration of Therapy**

Each patient will be on study therapy for six weeks starting with the day of brachytherapy.

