⁶ An appropriately trained and delegated study team member will contact subjects on treatment weekly to assess adverse event and concomitant medication information, to answer subject questions, and to ensure compliance with study medication and procedures. 30 days after the last dose of study drug, a study team member will contact subjects to assess adverse event information.

⁷ CBC with differential and platelets.

⁸ Complete Metabolic Panel including: Sodium, Potassium, Chloride, Carbon Dioxide, Alkaline Phosphatase, Aspartate Aminotransferase, Alanine Aminotransferase, Urea Nitrogen, Glucose, Creatinine, Calcium, Protein, Albumin, Bilirubin, Anion Gap.

⁹ Inflammatory markers include: erythrocyte sedimentation rate, C-reactive protein, prostate-specific antigen (PSA)

¹⁰ Questionnaires include: National Institutes of Health-Chronic Prostatitis Symptom Index (NIH-CPSI), The Expanded Prostate Cancer Index Composite (EPIC), The International Prostate Symptom Score (I-PSS), Rectal Function Assessment Score (R-FAS), The Sexual Health Inventory for Men (SHIM) Questionnaire.

¹¹ A Q-Urol/Placebo dosing diary will be dispensed on the day of brachytherapy and returned completed at the EOT visit (Appendix 6).

¹² Patients will be asked to maintain a diary of the daily use of medications taken for prostate pain for 28 days post-brachytherapy (Appendix 7).

¹³ Q-Urol/Placebo will begin after brachytherapy placement.

Version Date: 11APR2023

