11.6 Dosing and Pain Diary

Patients will be required to keep a diary of the Q-Urol/Placebo doses taken during the study. If a dose is missed or omitted, comments should be added to indicate why the dose was not taken.

Patients will also be required to keep a diary of any medications used for pain management for 28 days after brachytherapy placement. On the diary, subjects will be asked to indicate yes/no if they took any medications for the management of prostate-related pain during the day. They will be asked to record this information daily for 28 days post-brachytherapy.

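### The pain diary and its endpoint do not exclude the study capsules; men who count them would dilute the comparison, or bias it if their share differs by arm

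*Combined protocol and SAP*

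**What the plan says.** Section 1.2 defines the endpoint for objective 1.2.4 as "The number of days during the 28 days post-brachytherapy that any medication is taken for the treatment of prostate-related pain". Section 11.6 gives the procedure: "subjects will be asked to indicate yes/no if they took any medications for the management of prostate-related pain during the day". Footnote 12 of the Schedule of Events reads "Patients will be asked to maintain a diary of the daily use of medications taken for prostate pain for 28 days post-brachytherapy". The form in Appendix 7 opens with "Please record any use of me dications intended for the managemen t of prostate pain" (the split words come from reading the PDF). Each daily row asks about any medication, ending "ion today for prostate pain", and offers a Yes box and a No box. It has no field for the name of the drug. Section 13.2.3 item 4 takes the same count, summarises it by mean, median and interquartile range, and compares the arms with a Wilcoxon test. None of these five places excludes study treatment or defines which medications count.

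On the capsules, section 7.1 says "patients will self-administer two Q-Urol or placebo capsules by mouth with food twice daily", and section 7.4 says "Each patient will be on study therapy for six weeks starting with the day of brachytherapy". Section 7.2.2 calls them medication: "Subjects will be instructed to self-administer the medication at home orally twice daily". Sections 7.2.3 and 10.3 use the same word for capsules that are returned.

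Section 11.6 also requires a separate diary of study doses (Appendix 6). Footnote 6 of the Schedule of Events provides for weekly calls that collect concomitant medications.

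**The concern.** The capsules are given to reduce prostatitis symptoms, and objective 1.2.4 is about prostatitis-related pain. A man who thinks of his capsules as something taken for prostate pain can truthfully tick Yes every day, whatever his use of analgesics. Another man with the same analgesic use may leave the capsules out. The form leaves each patient to decide, and afterwards a capsule-only Yes looks the same as an analgesic Yes.

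At stake is the only endpoint for objective 1.2.4. If men in both arms count the capsules equally often, the difference between arms is diluted. If the share differs by arm, the difference is biased. One possible route is that men who feel better credit the capsules. Another is that men who count the capsules stop them early, and so switch from Yes to No for a reason other than analgesic need.

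**Working it through.** **1. The plan's own figures.** The documents state no effect size, power, alpha or sidedness for the diary endpoint, so there is nothing to reproduce for it. The figures in section 13.2.1 concern the primary endpoint. Simulating that two-stage rule (200,000 runs per hypothesis) gives power 90.0%, one-sided type I error 0.050, futility stopping 12.5% under the null and 0.3% under the alternative, and efficacy stopping 12.5% under the alternative. The stated values are 90%, 0.05, 12%, 0.3% and 12%. They reproduce, and they do not depend on the diary.

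**2. Overlap.** Capsules are scheduled for 6 × 7 = 42 days from the day of brachytherapy. The diary covers 28 days, all within that period, in both arms.

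**3. Dilution.** Let μ be an arm's true mean number of days with other pain medication. Let f be the share of men who count the capsules and so score 28, and suppose that counting is unrelated to true days. Then

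expected score = (1 − f)μ + 28f.

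With the same f in both arms the term 28f cancels:

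difference = (1 − f)(μ_control − μ_treatment).

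**4. Illustration, with assumed inputs.** Daily probabilities average 0.50 and 0.32, so the true means are 28 × 0.50 = 14.0 and 28 × 0.32 = 8.96 days, a difference of 5.04. Days are beta-binomial with concentration 2. There are 70 men per arm (section 4.3), a two-sided Wilcoxon test at 0.05 (assumed) and 3,000 simulated trials per row.

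| f, both arms | (1 − f) × 5.04 | Simulated difference | Power |
|---|---|---|---|
| 0% | 5.04 | 5.03 | 95% |
| 10% | 4.54 | 4.55 | 84% |
| 25% | 3.78 | 3.73 | 54% |
| 50% | 2.52 | 2.50 | 17% |
| 75% | 1.26 | 1.27 | 6% |
| 100% | 0 | 0 | no test possible |

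Power falls faster than the mean difference because the men at 28 also add spread and ties.

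Other assumed effects show the same pattern at f = 0, 10%, 20% and 30%. With true means of 14 and 9.5 days, power is 90%, 74%, 56% and 39%. With 8 and about 4.5 days (concentration 1.5), it is 87%, 72%, 51% and 33%.

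**5. Bias.** With no true difference and unequal shares, the spurious difference is (f_treatment − f_control)(28 − μ). With μ = 14:

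| f control / f treatment | Formula | Simulated | Rejections at nominal 5% |
|---|---|---|---|
| 10% / 20% | 0.10 × 14 = 1.4 days | 1.47 | 17% |
| 10% / 30% | 0.20 × 14 = 2.8 days | 2.81 | 51% |
| 25% / 40% | 0.15 × 14 = 2.1 days | 2.06 | 31% |

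**The case against.** The two-diary design points to the intended reading. Section 11.6 asks first for a diary of study doses and then for a further diary of pain medication, and a man who already logs each capsule on its own form has little reason to record it again. The capsules follow a fixed schedule rather than being taken in response to pain. Section 3.1 describes the product as a herbal supplement, and under blinding a man does not know whether his capsules are active. The word medication for the capsules comes from protocol text that patients may never see; the dosing diary speaks of capsules. What the consent form tells patients was not available for this review. The weekly calls would also help to identify an all-Yes diary with no analgesic on record.

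Much of this stands. It makes the narrower reading natural, so f may well be small. But the existence of a second form shows intent and does not instruct the patient. The dosing diary records that capsules were taken, not whether the man counted them in the other diary. The calls are a partial check only: they are weekly, the protocol does not say that they capture daily use, and it plans no comparison with the diary.

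A reader might go further and infer that the endpoint loses its contrast altogether. The documents do not support that. Total loss needs f = 100%, and nothing in the text shows that f is even above zero.

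**Conclusion.** The gap in wording is confirmed, and its severity is minor. All five places that define or collect this endpoint count any medication for prostate pain, and none excludes capsules that both arms are scheduled to take throughout the diary period. The supported consequence is conditional: dilution by the factor (1 − f) if men in both arms count the capsules equally often, and bias if they do not.

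The size is unknown, because the documents give neither f nor any planning figure for this endpoint. The power and rejection rates above rest on assumed means, dispersion, sidedness and values of f, and on counters scoring exactly 28. They show how sensitive the count would be; they do not forecast what will happen in this trial. The bias through early stopping of capsules needs both miscounting and unequal discontinuation, and it is not quantified here. The primary NIH-CPSI endpoint and the sample size are unaffected.

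**What to change.** In Appendix 7, add to the daily question the words *not counting your study capsules*. Put *other than study treatment* in the matching text of sections 1.2.4, 11.6 and 13.2.3 item 4 and in Schedule of Events footnote 12.

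For diaries already completed on the present form, compare the all-Yes diaries with the weekly concomitant-medication records before unblinding, and report the result as a sensitivity check. A test stratified by form version is not needed.

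The cost is one form revision with IRB approval, matching protocol wording, and possibly two diary versions if enrolment has begun. Treatment, visits and sample size do not change.

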Appendix 8: NCCN Risk Stratification

Risk Group	Clinical Pathologic Features				
Very Low	T1c AND				
	Gleason Score ≤ 6/ grade group 1 AND				
	• PSA < 10 ng/mL AND				
	• Fewer than 3 prostate biopsy fragments/cores, positive, ≤ 50% cancer in each fragment/core ^b AND				
	• PSA density < 0.15 ng/mL/g				
Low	• T1-T2a AND				
	Gleason score ≤ 6/grade group 1 AND				
	• PSA < 10 ng/mL				
Favorable Intermediate	• T2b – T2c OR				
	• Gleason score 3 + 4 = 7/grade group 2 OR				
	• PSA 10-20 ng/mL				
	AND				
	• Percentage of positive biopsy cores < 50%				
Unfavorable Intermediate	● T2b – T2c OR				
	• Gleason score 3 + 4 = 7/grade group 2 or Gleason score 4 + 3 = 7/grade group 3 OR				
	• PSA 10-20 ng/mL				
High	• T3a OR				
	• Gleason score 8/grade group 4 or Gleason score 4 + 5 = 9/grade group 5 OR				
	• $PSA > 20 \text{ ng/mL}$				
Very High	• T3b – T4 OR				
	Primary Gleason pattern 5 OR				
	• > 4 core with Gleason score 8-10/ grade group 4 or 5				
Regional	Any T, N1, M0				
Metastatic	Any T, Any N, M1				

Short Title: Q-Urol	Subject ID
Version Date: 11APR2023	

Subject ID:	Subject Initials:
	Date:

	Appendix 9 Baseline Characteristics				
1.	Does the patient have a history of Coronary Artery Disease? Yes□ No□				
2.	Has the patient had bacterial prostatitis that went away with antibiotics? Yes□ No□				
3.	Does the patient have any family history of prostatitis? Yes□ No□				
4.	Alcohol history:				
	☐ Never used alcohol				
	☐ Current alcohol user				
	☐ Former alcohol user				
5.	Smoking history:				
	☐ Never smoked				
	☐ Current smoker				
	 Average number of packs per day 				
	 Number of years smoked 				
	☐ Former smoker				
	 Average number of packs per day 				
	 Number of years smoked 				
6.	Employment status				
	□ Employed				
	☐ Retired				
	☐ Student				
	□ Unknown				
	□ Other				
7.	Insurance status				
	☐ Private insurance				
	☐ Medicare				
	☐ Medicaid				
	□ VA				
	☐ Military				
	□ Not insured				
	☐ Self pay				
	□ Unknown				
	Other				

Version Date: 11APR2023

Appendix 10: Charlson Comorbidity Index

Date of Assessment:			_	S	tudy Pa	tient	ID:			
				S	tudy Pa	tient	Init	tials:		
Instructions : Select one option per line.										
		Non	ıe	Unco	omplica	ted	E	nd-o	rgan Da	mage
Diabetes mellitus										
							l			
					None	Mi	ld	Mo	derate/S	Severe
Liver disease										
					•		i i			
	No	ne			mia, Ly lized So				Metas Solid T	
Malignancy – exclude basal cell carcinoma										
									Yes	No
HIV or AIDS										
Moderate to severe chronic kidney disease	;									
Congestive heart failure										
Myocardial infarction										
Chronic obstructive pulmonary disease (C	OPI	D)								
Peripheral vascular disease										
Cerebrovascular accident (CVA) or transic	ent i	sche	mic	attacl	k (TIA)					
Dementia										
Hemiplegia										
Connective tissue disease										
Peptic ulcer disease										
Investigator Signature										

Version Date: 11APR2023

Appendix 11: Eastern Cooperative Oncology Group Performance Status Criteria (ECOG) & Karnofsky Performance Scale Index (KPS) equivalency

ECOC	G Performance Status Scale ¹	Karnofsky Performance Scale ²		
Grade	Descriptions	Percent	Description	
0	Normal activity. Fully active, able to carry on all pre-disease		Normal, no complaints, no evidence of disease.	
	performance without restriction.	90	Able to carry on normal activity; minor signs or symptoms of disease.	
1	Symptoms, but ambulatory. Restricted in physically strenuous activity, but ambulatory and able to	80	Normal activity with effort; some signs or symptoms of disease.	
1	carry out work of a light or sedentary nature (e.g., light housework, office work).	70	Cares for self, unable to carry on normal activity or to do active work.	
	In bed < 50% of the time. Ambulatory and capable of all self-		Requires occasional assistance, but is able to care for most of his/her needs.	
2	care, but unable to carry out any work activities. Up and about more than 50% of waking hours.	50	Requires considerable assistance and frequent medical care.	
3	In bed >50% of the time. Capable of only limited self-care, confined	40	Disabled, requires special care and assistance.	
3	to bed or chair more than 50% of waking hours.	30	Severely disabled, hospitalization indicated. Death not imminent.	
4	4 100% bedridden. Completely disabled. Cannot carry on any self-care. Totally confined to bed or chair.		Very sick, hospitalization indicated. Death not imminent.	
7			Moribund, fatal processes progressing rapidly.	
5	Dead.	0	Dead.	

Version Date: 11APR2023

